## **6.6. Interim Analyses and Data Monitoring**

See Section [6.2](#).

## **6.7. Multicenter Studies**

Data will be pooled across all clinical sites for analyses. Center effects are not anticipated because the sites are using standardized procedures for vaccination and assessment of solicited and unsolicited adverse events, and the study relies on central laboratories for the assessment of immunogenicity endpoints.

## **6.8. Multiple Comparisons/Multiplicity**

No formal hypothesis testing will be conducted.

## 7. STUDY PARTICIPANTS

### 7.1. Disposition of Participants

The disposition of participants in the study will be tabulated by vaccination arm ([Table 19](#), [Table 20](#), [Table 21](#), [Table 22](#), [Table 23](#), and [Table 24](#)). The table shows the total number of participants screened, enrolled, receiving first vaccination, receiving the second vaccination (if applicable), discontinuing treatment, terminated from study follow-up, and completing the study. The composition of analysis populations, including reasons for participant exclusion, by treatment arm, is presented in [Table 25](#), [Table 26](#), [Table 27](#), [Table 28](#), and [Table 29](#). A summary of the reasons that participants were screened but not enrolled will be presented in [Table 36](#). A flowchart showing the disposition of study participants, adapted from the Consort Statement [3] will be included ([Figure 1](#) and [Figure 2](#)). This figure will present the number of participants screened, enrolled, lost to follow-up, and analyzed, by vaccination arm. A listing of participants who discontinued dosing or terminated from study follow-up and the reason will be included in [Listing 2](#).

### 7.2. Protocol Deviations

A summary of participant-specific protocol deviations will be presented by the reason for the deviation, the deviation category, and the vaccination arm for all deviations ([Table 9](#), [Table 10](#), [Table 11](#), [Table 12](#), and [Table 13](#)) and major deviations only ([Table 14](#), [Table 15](#), [Table 16](#), [Table 17](#), and [Table 18](#)). Ineligibility or product administration deviations will be considered major deviations and reviewed for possible participant exclusion from the per protocol population. Other protocol deviations may be considered major deviations, as determined by DMID. All participant specific protocol deviations and non-participant specific protocol deviations will be included in [Listing 3](#) and [Listing 4](#).

## 8. IMMUNOGENICITY EVALUATION

### 8.1. Primary Immunogenicity Analysis

See Section 9 for safety analyses which are the primary endpoints of this study.

### 8.2. Secondary Immunogenicity Analyses

Descriptive summaries of immunogenicity data will be presented for the mITT and PP populations.

The results of three immunological assays will be analyzed to address the secondary immunogenicity endpoints. The ELISA assay is a validated assay that reports antibody concentrations and is used to assess antibody binding against SARS-CoV-2 S-2P and ribosomal binding domain (RBD). The results of the ELISA assay will be summarized for each group at each available time point by the geometric mean (GM) and geometric mean fold rise (GMFR) from baseline (Day 1) along with corresponding 95% confidence intervals (CIs). GMFR is defined as the ratio of the result at a time point divided by the result at Day 1. Summaries of the ELISA results are shown starting with [Table 48](#) and ending with [Table 71](#). Graphical displays will include geometric mean over time (starting with [Figure 3](#) and ending with [Figure 22](#)), and distribution of responses over time (starting with [Figure 143](#) and ending with [Figure 162](#)).

The SARS-CoV-2 pseudovirus neutralization assay (PsVNA) and focus reduction neutralization test (FRNT) will be run using serial dilutions against available variants (e.g. Beta, Delta, Omicron). From these assays ID50 and ID80, which estimate the amount of antibodies required for a neutralization rate of 50% or 80%, will be reported. Neutralization titers will be summarized by the GM, GMFR, geometric mean ratio (GMR) to D614G, and seropositive rate with corresponding 95% CIs, for each group at each time point. The GMR is the geometric mean of the assay result against a variant of concern divided by the result against D614G. The seropositive rate is the percentage of participants with results above the LLOD. The summaries of PsVNA results are shown starting with [Table 72](#) and ending with [Table 131](#), and the summaries of FRNT results are shown starting with [Table 132](#) and ending with [Table 191](#). Graphical displays for PsVNA and FRNT will include geometric mean over time (starting with [Figure 23](#) and ending with [Figure 142](#)) and distributions of responses over time (starting with [Figure 163](#) and ending with [Figure 282](#)).

T cell responses to ChAd-S or ChAd-S-TCE, and SAM-S or SAM-S-TCE will be assessed by IFN- $\gamma$  ELISpot and ICS assays. The results of the IFN- $\gamma$  ELISpot assay will be summarized at all available time points in tables (starting with [Table 192](#) and ending with [Table 201](#)) by the mean with a 95% CI, median, min, and max and in figures showing the distribution of responses over time (starting with [Figure 283](#) and ending with [Figure 392](#)). The results of the ICS assay will be summarized at all available time points in tables (starting with [Table 202](#) and ending with [Table 211](#)) by the mean with a 95% CI, median, min, max, and response rate with a 95% CI. The distribution of results over time and the response rate will be presented in figures, starting with [Figure 393](#) and ending with [Figure 542](#). For the ICS assay, results below 0.001 will be imputed as 0.001.

CIs for means, GMs, GMFRs, and GMRs will be calculated using the Student's t-distribution and CIs for seropositive rates and response rates will be calculated using the Clopper-Pearson binomial method.

If additional immunological assays are determined to be necessary, then the results will be summarized in a similar manner to that of the assays described above.

Individual immunogenicity responses are shown in [Listing 8](#).

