## 2. INTRODUCTION

This phase 1 clinical trial will explore the ability of novel vectors (notably self-amplifying mRNA or SAM), a novel schedule (heterologous or homologous prime-boost), and novel SARS-CoV-2 epitope cassettes (extending COVID antigenic vaccine content beyond Spike) to safely drive strong, broad, durable immune responses to SARS-CoV-2. Cassette S contains a codon optimized Spike and will be assessed during Stage 1. An additional Spike-T Cell Epitope (S-TCE) cassette will also be studied in Stage 1 as well as in Stage 2.

The successful emergency use authorization (EUA)/licensed COVID-19 vaccine roll-out campaign has resulted in a diminishing domestic naïve population. Most of the population has received an EUA/licensed mRNA COVID-19 vaccine; to optimize homogeneity of study groups, we focus on the enrollment of EUA/licensed mRNA COVID-19 vaccine experienced participants into the majority of Stage 2 Groups. Due to the rare cases of Thrombosis and Thrombocytopenia Syndrome (TTS) associated with the approved AstraZeneca and EUA Johnson & Johnson/Janssen adenovirus vectored COVID-19 vaccines in patients primarily <50 years old, we will focus on boosting participants >60 years old with Chimpanzee Adenovirus (ChAd)-S-TCE. In addition, ChAd-S-TCE vaccine may be a stronger T cell response inducer than the SAM-S-TCE vaccine, particularly in the elderly, which further supports boosting of participants >60 years old.

Because the EUA/licensed COVID-19 vaccines encode only the Spike protein, a single boost with ChAd-S-TCE or SAM-S-TCE will boost spike-specific T cell immunity yet may only prime a TCE-specific response in previously vaccinated participants. Ongoing studies suggest increased receipt of additional doses of mRNA COVID-19 vaccines may increase reactogenicity in persons previously vaccinated with mRNA COVID-19 vaccines. Therefore, participants who previously received two EUA/licensed mRNA COVID-19 vaccines will receive one boost of SAM-S-TCE, whereas participants previously given at least one dose of the Johnson & Johnson/Janssen Ad26 COVID-19 EUA plus one booster dose of EUA/licensed mRNA COVID-19 vaccine will receive two boosts of SAM-S-TCE to determine whether the TCE-specific response can be enhanced.

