**Table 1: Objectives and Endpoints**

Objectives	Endpoints (Outcome Measures)
Primary	
 
To assess the safety and tolerability of different doses of ChAd-S or ChAd-S-TCE, and SAM-S or SAM-S-TCE when administered as: 
 
prime-boost in healthy naïve adult participants
 
boost in healthy adult participants previously vaccinated with an EUA/licensed mRNA or adenoviral-vectored COVID-19 vaccine
 
 
 

Secondary	
 
To assess the humoral immunogenicity of ChAd-S or ChAd-S-TCE, and SAM-S or SAM-S-TCE 
 
Response rate, and magnitude of SARS-CoV-2-specific antibody binding and neutralization titers (including against emergent viral strains, e.g., B.1.1.7) in serum samples will be assessed via a range of assays measuring total Spike-specific IgG (ELISA-based), and function (neutralization, RBD binding, or similar) in serum on the following days: 
 
For Stage 1, Groups 1 and 3A: Days 1 and 29 post Dose 1; then Days 29, 181, and 366 post Dose 2
 
For Stage 1, Groups 3B and 4: Days 1, 29, 57, and 85-130 post Dose 1; then Days 15, 29, 85, 181, and 366 post Dose 2
 
For Stage 2, Groups 5-7A*, 7B*, 9, 10A, 10B, and 11A, 11B, and 13-15: Days 1, 15, 29, 85, 181, and 366 post study vaccination
 
For Stage 2, Groups 8A*, 8B* and 12A*, 12B*: Days 1, 15, 29, and 57 post Dose 1; then Days 15, 29, 85, 181, and 366 post Dose 2
 
 
 
 
 

 
To assess T cell responses to ChAd-S or ChAd-S-TCE, and SAM-S or SAM-S-TCE
 
	
 
Response rate, magnitude, and functional profiling of SARS-CoV-2 specific T cells stimulated with overlapping 15mers covering Spike and TCE regions from all participants at pre- and post-treatment timepoints will be analyzed by IFN-<math>\gamma</math> ELISpot: 
 
For Stage 1, Groups 1 and 3A: Days 1 and 29 post Dose 1; then Days 29, 181, and 366 post Dose 2
 
For Stage 1, Groups 3B and 4: Days 1, 29, and 85-130 post Dose 1; then Days 15, 29, 85, 181, and 366 post Dose 2
 
For Stage 2, Groups 5-7A*, 7B*, 9, 10A, 10B, 11A, 11B, and 13-15: Days 1, 15, 29, 85, 181, and 366 post study vaccination
 
 
 

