## 14.2 Immunogenicity Data

**Table 52: Summary of ELISA IgG Antibody Against SARS-CoV-2 S-2P by Time Point and Vaccination Arm – COVID-19 Vaccination Naïve, 18-60 years of age, Groups 1 and 3A, mITT Population**

Time Point	Statistic	Group 1: $5 \times 10^{10}$ vp ChAd-S/30 µg SAM-S (N=X)	Group 3A: 30 µg SAM-S/30 µg SAM-S (N=X)	All Participants (N=X)
Day 1 (Pre-Vaccination 1)	n			
	GMT			
	95% CI			
Day 29 Post Vaccination 1	n			
	GMT			
	95% CI			
Day 57 Post Vaccination 1 (29 Days Post Vaccination 2)	n			
	GMT			
	95% CI			
Day 209 Post Vaccination 1 (181 Days Post Vaccination 2)	n			
	GMT			
	95% CI			
Day 391 Post Vaccination 1 (366 Days Post Vaccination 2)	n			
	GMT			
	95% CI			

Notes: N = Number of participants enrolled  
n = Number of participants in the mITT population with available results  
GMT = Geometric Mean Titer

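### The antibody response rate has no analysis for ELISA and ignores Day 1 for neutralization, and the ELISA table shell omits the fold rise that Section 8.2 requires

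*SAP*

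**What the plan says.** - **Endpoint.** Table 1 (Objectives and Endpoints) lists as a secondary humoral endpoint "Response rate, and magnitude of SARS-CoV-2-specific antibody binding and neutralization titers". A rate and a magnitude are therefore both promised, for binding and for neutralizing antibody.
- **ELISA text.** Section 8.2 says ELISA results will be "summarized for each group at each available time point by the geometric mean (GM) and geometric mean fold rise (GMFR) from baseline", with 95% CIs. It names no rate.
- **ELISA shell.** Table 52 is titled "Summary of ELISA IgG Antibody Against SARS-CoV-2 S-2P by Time Point and Vaccination Arm". At every visit its rows are n, GMT and 95% CI, and its footnote defines GMT but not GMFR. Tables 53-71 follow the same format.
- **Neutralization text.** Section 8.2 says "Neutralization titers will be summarized by the GM, GMFR, geometric mean ratio (GMR) to D614G, and seropositive rate with corresponding 95% CIs". The rate is then defined: "The seropositive rate is the percentage of participants with results above the LLOD".
- **Neutralization shell.** Table 72 shows seropositivity at Day 1 and at later visits, and GMFR at every post-dose visit.
- **Population.** Section 2 says "we focus on the enrollment of EUA/licensed mRNA COVID-19 vaccine experienced participants into the majority of Stage 2 Groups", and notes that those vaccines encode Spike only. The footnotes to Table 2 also allow prior infection in Groups 10, 11 and 13-15.

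**The concern.** A response rate should say how many participants responded to the study vaccine. For binding antibody no such quantity is planned, although Table 1 names one. For neutralizing antibody the planned quantity is a status at a visit, not a change. It can work in the naive Stage 1 groups, where a value above the LLOD after dosing is new. In Stage 2, a participant who was above the LLOD on Day 1 counts as positive whether the study vaccine raised the titer tenfold or not at all.

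Section 8.2 itself treats the two ideas as distinct. Its sentence on confidence intervals lists seropositive rates and response rates separately, and within that section only the ICS assay is given a response rate.

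Section 2 says the trial is meant to pick the vector, cassette, schedule and dose with the strongest T and B cell responses. The study is open-label (Section 4.4.6), and Section 6.2 allows immunogenicity to be reviewed and shared by group before the final analysis. A responder rule left open could therefore be settled after results are known.

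**Working it through.** **1. Stage 2 share, from Table 2.** Groups 7, 8 and 12 were not enrolled. The rest are Groups 5 (10), 6 (10), 9 (8), 10 (8-12), 11 (8-12) and 13-15 (7-10 each).
- Low: 10 + 10 + 8 + 8 + 8 + 3×7 = 65.
- High: 10 + 10 + 8 + 12 + 12 + 3×10 = 82.
- With 17 in Stage 1, the totals are 82 and 99.

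**2. The plan's own precision figure.** Table 5 uses GMT × exp(± t(0.975, n−1) × SD/√n) on the log_e scale. At GMT 100 and n = 10 this gives (69.9, 143.0) for SD 0.5 and (48.9, 204.5) for SD 1.0, as printed. The Table 5 intervals at GMT 100 reproduce for all four n and both SDs.

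**3. Ceiling on the neutralization rate.** The largest possible rise is 100% minus the Day 1 rate. The SAP gives no Day 1 rate, so a range is assumed.

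| Assumed Day 1 rate | Largest rise (points) | Able to convert, of 10 |
|---|---|---|
| 50% | 50 | 5 |
| 80% | 20 | 2 |
| 90% | 10 | 1 |
| 100% | 0 | 0 |

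If every participant is positive, the Clopper-Pearson lower limit is 0.025^(1/n): 59.0% for n = 7, 63.1% for n = 8, 69.2% for n = 10 and 73.5% for n = 12. The interval depends on n alone, so an all-positive arm reads the same at any dose and at Day 1.

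**4. Where a ceiling is plausible.** Tables 72-191 are 120 neutralization tables. D614G takes 40 of them (72-91 and 132-151), and half of those are ID50, which leaves 20. The other 100 are ID80 or an Omicron-lineage variant, where Day 1 values may be below the LLOD and the rate could move.

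**5. What GMFR can show.** Take the Table 5 SDs as the SD of the log fold rise. This is an assumption: with equal pre- and post-dose SDs, the variance is 2·SD²·(1−ρ), which equals SD² at ρ = 0.5. The 95% CI for GMFR then excludes 1 when the observed GMFR exceeds exp(t × SD/√n):
- n = 10: 1.43 (SD 0.5) or 2.05 (SD 1.0).
- Extremes: 1.37 (n = 12, SD 0.5) to 2.52 (n = 7, SD 1.0).

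**6. What a Day 1-referenced rate would do.** As an illustration, define response as a rise of at least 4-fold with a log-normal fold rise, so that P = 1 − Φ((ln 4 − ln GMFR)/SD).

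| True GMFR | SD 0.5 | SD 1.0 |
|---|---|---|
| 1 | 0.3% | 8% |
| 2 | 8% | 24% |
| 4 | 50% | 50% |
| 8 | 92% | 76% |

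Unlike the LLOD rate, this one moves with the boost and is not capped by the proportion already positive on Day 1.

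**7. Text against shell.** Section 8.2 requires GMFR for ELISA and for neutralization. Table 72 has the row and Table 52 does not, which points to an omission. Programmed literally, Tables 52-71 (20 tables) would show group GMTs by visit and no within-participant change.

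**The case against.** The strongest case on the other side is that the endpoint pairs rate with magnitude, and magnitude is well served. Section 8.2 plans GMFR from Day 1 with a CI for ELISA, PsVNA and FRNT. The Table 72 shell prints Day 1 seropositivity, so any ceiling would be visible. No hypothesis is tested (Section 6.8), and dichotomising 7-12 people loses information: under the assumptions in the working, a true 2-fold boost gives only 8-24% responders by a 4-fold rule, while at n = 10 and SD 0.5 an observed 2-fold GMFR already excludes 1. The 4-fold threshold also appears nowhere in the SAP.

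Most of this stands, and it rules out three stronger readings that a reader might infer.
- **That the secondary endpoint cannot show a boost.** It can, through GM and GMFR. Only the rate component is weak.
- **That the rate will sit near 100% in every arm at every visit.** No baseline rate is given, and ID80, the Omicron-lineage variants and late visits may leave room to move. Nor does the SAP say how many Stage 2 participants were previously infected.
- **That no ELISA table contains any measure of response.** Table 52 prints GMT at Day 1 and later, Figures 3-22 and 143-162 show ELISA results over time, and Listing 8 gives individual values. What the tables lack is a baseline-referenced measure.

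The objection does not supply the missing ELISA rate, give the neutralization rate a reference to Day 1, or restore the GMFR row.

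**Conclusion.** The point holds for the rate component and for the ELISA shell. Three facts rest on the SAP alone: a promised ELISA response rate has no analysis; the neutralization rate cannot register a response in a Stage 2 participant already above the LLOD on Day 1; and Table 52 contradicts Section 8.2 by omitting GMFR.

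The size of the ceiling is an assumption: a possible rise of 0-50 points for Day 1 rates of 100% down to 50%, with the low end most plausible for D614G ID50. GMFR remains able to show a boost of roughly 1.4- to 2.5-fold or more, if the Table 5 SDs apply to the log fold rise. This should be corrected before the final analysis, but the trial's ability to describe antibody responses does not depend on it.

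**What to change.** 1. Add GMFR (95% CI) rows at each post-dose visit to the Table 52 shell, and so to Tables 53-71, to match Section 8.2 and Table 72.
2. In Section 8.2, define a seroresponse relative to the participant's own Day 1 value for S-2P and RBD ELISA, PsVNA and FRNT. A rise of at least 4-fold is one example; the sponsor may justify another threshold. Fix it before the final analysis. Because interim results may already have been seen, give the reason for the choice.
3. Set values below the LLOD to half the LLOD, as in Section 6.5. With a 4-fold rule, a participant below the LLOD on Day 1 then needs 4 × 0.5 = 2 times the LLOD to count.
4. Report x/n with a Clopper-Pearson CI per arm and time point, and add the row to the Table 52 and Table 72 shells.
5. Keep the seropositive rate as a descriptive row. It serves as a response rate in the naive Stage 1 groups. Keep GMFR as the main measure of boost.

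The cost is SAP and shell wording, one derived variable from data already planned, and a few table rows. The responder rate discards some information in groups of about 7-12, which GMFR retains.

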### 3.1. Study Definitions and Derived Variables

Vital signs, including oral temperature, pulse, and blood pressure (BP), and clinical laboratory parameters obtained prior to the first study vaccination will be considered as baseline. Blood drawn for cellular immunology assays, antibody assays, and transcriptomal assays (groups 5-11, 13-15 only) prior to the first dose of study product will be considered as baseline in immunogenicity analyses.

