**Table 187:** **Summary of Focus Reduction Neutralization Test ID80 Against SARS-CoV-2 BA.5 by Time Point and Vaccination Arm - COVID-19 mRNA Vaccinated, >60 years of age, SAM-S-TCE Boosts, Per Protocol Population**

**Table 188:** **Summary of Focus Reduction Neutralization Test ID50 Against SARS-CoV-2 BA.5 by Time Point and Vaccination Arm - COVID-19 mRNA Vaccinated, >60 years of age, ChAd-S-TCE Boosts, mITT Population**

**Table 189:** **Summary of Focus Reduction Neutralization Test ID50 Against SARS-CoV-2 BA.5 by Time Point and Vaccination Arm - COVID-19 mRNA Vaccinated, >60 years of age, ChAd-S-TCE Boosts, Per Protocol Population**

**Table 190:** **Summary of Focus Reduction Neutralization Test ID80 Against SARS-CoV-2 BA.5 by Time Point and Vaccination Arm - COVID-19 mRNA Vaccinated, >60 years of age, ChAd-S-TCE Boosts, mITT Population**

**Table 191:** **Summary of Focus Reduction Neutralization Test ID80 Against SARS-CoV-2 BA.5 by Time Point and Vaccination Arm - COVID-19 mRNA Vaccinated, >60 years of age, ChAd-S-TCE Boosts, Per Protocol Population**

**Table 192: Summary of T Cells Expressing IFN $\gamma$  as measured by the ELISpot Assay in Spot Forming Units (SFU) per Million by Time Point and Vaccination Arm – COVID-19 Vaccination Naïve, 18-60 years of age, Groups 1 and 3A, mITT Population**

Overlapping Peptide	Time Point	Statistic	Group 1: $5 \times 10^{10}$ vp ChAd-S/30 $\mu$ g SAM-S (N=4)	Group 3A: 30 $\mu$ g SAM-S/30 $\mu$ g SAM-S (N=3)
15mer OLPs Spanning Membrane Frame	Day 1 (Pre-Vaccination 1)	n	x	x
		Mean (95% CI)	x.xx (x.xx, x.xx)	x.xx (x.xx, x.xx)
		Median	x.xx	x.xx
		Min, Max	x.x, x.x	x.x, x.x
	Day 29 Post Vaccination 1	n		
		Mean (95% CI)		
		Median		
		Min, Max		
	Day 57 Post Vaccination 1 (29 Days Post Vaccination 2)	n		
		Mean (95% CI)		
		Median		
		Min, Max		
15mer OLPa Spanning Nucleocapsid Frame	Day 1 (Pre-Vaccination 1)	n		
		Mean (95% CI)		
		Median		
		Min, Max		
	Day 29 Post Vaccination 1	n		
		Mean (95% CI)		
		Median		
		Min, Max		
	Day 57 Post Vaccination 1 (29 Days Post Vaccination 2)	n		
		Mean (95% CI)		
		Median		
		Min, Max		

Overlapping Peptide	Time Point	Statistic	Group 1: $5 \times 10^{10}$ vp ChAd-S/30 µg SAM-S (N=4)	Group 3A: 30 µg SAM-S/30 µg SAM-S (N=3)
15mer OLPs spanning Open Reading Frame 3a	Day 1 (Pre-Vaccination 1)	n		
		Mean (95% CI)		
		Median		
		Min, Max		
	Day 29 Post Vaccination 1	n		
		Mean (95% CI)		
		Median		
		Min, Max		

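### The T cell tables give per-visit values only, so in Stage 2 the change from each participant's own Day 1 has no interval and can mix different participants

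*SAP*

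**What the plan says.** For ELISpot, Section 8.2 plans a summary at all available time points "by the mean with a 95% CI, median, min, and max and in figures showing the distribution of responses over time". For ICS it plans one "by the mean with a 95% CI, median, min, max, and response rate with a 95% CI". The shells have the same structure. Table 192 (ELISpot) has rows by peptide pool and visit for n, mean with CI, median, and minimum and maximum. Table 202 (ICS) has rows by visit for n, mean, CI, response rate and CI, and omits the median and range that the text promises. Neither shell has a difference, fold-rise or change row. The remaining T cell tables, up to Table 211, follow these two formats.

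Other parts of the plan do use Day 1 as a comparator:

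- Section 3.1 says that blood drawn for the cellular and antibody assays "prior to the first dose of study product will be considered as baseline in immunogenicity analyses".
- For ELISA, Section 8.2 plans a geometric mean fold rise: "GMFR is defined as the ratio of the result at a time point divided by the result at Day 1". For the neutralization assays it says: "Neutralization titers will be summarized by the GM, GMFR, geometric mean ratio (GMR) to D614G, and seropositive rate with corresponding 95% CIs". (The Table 72 shell has the GMFR row. The Table 52 ELISA shell does not.)
- Section 9.6 summarizes change from baseline for the clinical laboratory results.

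The Introduction says what is expected of the T cells in Stage 2: "a single boost with ChAd-S-TCE or SAM-S-TCE will boost spike-specific T cell immunity yet may only prime a TCE-specific response in previously vaccinated participants".

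**The concern.** Stage 2 participants have already received licensed Spike vaccine, so Spike T cells are expected at Day 1. Previously infected participants can also carry T cells to Membrane, Nucleocapsid and ORF3a. A post-dose mean therefore combines what was there before with what the study dose added. The boost of Spike responses and the priming of TCE responses are both changes from Day 1, and the plan sets no statistic for a change.

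Comparison of dose groups makes this more important. Assignment is not randomized, Table 2 leaves the numbers of infected and noninfected participants open, Table 37 allows for two prior vaccination histories, and the shells of Tables 33-35 place first dosing between September 2021 and September 2022. Day 1 T cell levels can differ between groups for reasons unrelated to dose. Section 2 intends the trial to identify the vector, cassette, schedule and dose with the strongest T and B cell responses.

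**Working it through.** **1. What the planned rows can give.** Let A be the participants with a Day 1 result and B those with a post-dose result. If A and B are the same people, the post-dose mean minus the Day 1 mean equals the mean paired change. If B is a subset of A:

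mean over B of post − mean over A of Day 1 = mean over B of (post − Day 1) + [mean over B of Day 1 − mean over A of Day 1].

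The bracket reflects who remains, not the vaccine. It can be nonzero under this plan. Section 6.3.2 removes single visits (after a deviation, outside vaccine or infection, or when out of window), Section 6.5 imputes no missing data, and Section 4.5 allows T cell assays at a subset of the listed time points. Section 6.3.1 requires pre- and post-dose immunogenicity results, but not specifically T cell results.

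**2. What they cannot give.** For n complete pairs the variance of the mean change is (s1² + s2² − 2·r·s1·s2)/n. The two SDs can be recovered from the per-visit CIs. The correlation r appears in no planned table, so the CI of the change cannot be rebuilt.

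**3. The plan's own precision figure.** Table 5 uses exp(ln GMT ± t(0.975, n−1)·SD/√n). For GMT 100, SD 1.0 and n = 10: 2.262 × 1.0/√10 = 0.715, exp(0.715) = 2.045, giving (48.9, 204.5) as stated. All eight Table 5 intervals for GMT 100 reproduce.

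**4. Illustration of the gain.** The SAP states no SD or correlation for T cells. Assumed here: log SD 1.0 or 0.5 (the two antibody values of Table 5) and r from 0.5 to 0.9. The estimate is divided and multiplied by these factors:

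- Paired: exp(t(0.975, n−1)·SD·√(2(1−r))/√n)
- Unpaired: exp(t(0.975, 2n−2)·SD·√(2/n))

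At SD 1.0 and n = 10, unpaired: 2.101 × 0.447 = 0.940, factor 2.56. Paired at r = 0.7: 0.715 × √0.6 = 0.554, factor 1.74.

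| SD, n | Unpaired | Paired r = 0.5 | r = 0.7 | r = 0.9 |
|---|---|---|---|---|
| 1.0, 10 | 2.56 | 2.04 | 1.74 | 1.38 |
| 1.0, 7 | 3.20 | 2.52 | 2.05 | 1.51 |
| 0.5, 10 | 1.60 | 1.43 | 1.32 | 1.17 |

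At r = 0.3 (SD 1.0, n = 10) the paired factor is 2.33, still below 2.56. At r = 0 it is 2.75, slightly worse. A reader who compares two separate visit intervals by eye would need geometric means more than 2.045² = 4.18-fold apart before the intervals stop overlapping.

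**5. Scope.** Tables 192-201 and 206-211 plus 202-205 make 20. Stage 2 accounts for 196-201 and 206-211, that is 6 + 6 = 12. The other 8 cover vaccination-naïve Stage 1 groups.

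**The case against.** The best defence is that the plan does what its endpoint asks. Table 1 names response rate, magnitude and functional profile of T cells before and after treatment. It does not promise a change from Day 1. The boost-and-prime sentence is background in the Introduction, and Section 6.8 rules out formal testing. This stands: it is a gap in the analysis and does not contradict the endpoint.

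A reader might also infer that the T cell boost is not estimated at all, or that pre-existing immunity would pass unseen as vaccine effect. The documents do not support that. Day 1 is a row in the same table for the same pool, so a high starting mean is visible, and with complete data the mean change follows by subtraction. Figure notes mark prior infection on the ICS plots, and Listing 8 carries individual values. The loss is narrower: the interval, and a valid comparison when the participants at the two visits differ.

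The ICS response rate does not close the gap. The Table 202 shell reports it at Day 1 too, so it is a status at each visit, and this document gives no criterion for response. The figure images are not shown. Their titles and notes mention distributions, not change.

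The numerical gain is fairly called hypothetical. It uses an antibody SD and an assumed correlation on the log scale, while the plan summarizes T cells by arithmetic means. It does not show that a 2-fold boost would be resolved: at r = 0.7 the lower limit is 2/1.74 = 1.15, but at r = 0.5 it is 2/2.04 = 0.98.

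**Conclusion.** The point holds for the 12 Stage 2 T cell tables. As planned, they give no interval for the change from Day 1, and the Day 1 and post-dose means can cover different participants once visits are missing or excluded. Both follow from Section 8.2 and the shells without any assumption. The precision gain is illustrative: at log SD 1.0 and n = 10, a factor of 2.04 to 1.38 paired against 2.56 unpaired. It depends on Day 1 and post-dose values being positively correlated, which is plausible in participants with existing Spike immunity but is not stated in the SAP.

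The descriptive nature of the trial does not remove the point, because the antibody fold rise is equally descriptive. The omission invalidates no planned output, and in vaccination-naïve Stage 1 it matters less. The change is worth making because T cell response is a secondary objective and Day 1 blood for both assays is already scheduled.

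**What to change.** In Section 8.2 and the Stage 2 T cell tables (196-201 and 206-211; optionally Stage 1 as well), add for each post-Day-1 visit and peptide pool the paired change from Day 1, in participants with both results, with their number shown:

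- **ELISpot and ICS:** mean paired difference with t-based 95% CI, and median (minimum, maximum).
- **ELISpot also:** geometric mean fold rise with 95% CI, with the number of Day 1 values imputed at half the LLOD/LLOQ under Section 6.5. Where most Day 1 values are at that floor, as may occur for TCE pools, rely on the difference, because the ratio would largely reflect the imputed value.
- **ICS:** no fold rise, since the 0.001 floor in Section 6.5 would have the same effect.

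State in Section 8.2 that the Spike-boost and TCE-prime descriptions are read from these rows. The cost is one derived variable and a few added rows per visit. No new samples or visits are needed, and Section 8.2 already specifies t-based intervals.
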